### 3.2.4 Baseline definition

Unless otherwise specified, baseline values are defined as the last measurement obtained during the screening period or before the first administration of the study drug.

### 3.2.5 Data derivation and transformation

Age (years)=(Date of informed consent–Date of birth+1)/365.25. The result will be rounded down to the nearest integer.

## 3.3 Multiplicity

This study does not involve early termination due to efficacy during interim analysis. Therefore, there are no issues related to multiplicity.

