10.1 Sample size calculation

Currently, no large-scale RCTs exist in this field. The sample size calculation for this study is based on the results of the RESCUE-RE registry study in the Chinese population^[25], which reported that the proportion of patients achieving a mRS score ≤ 2 at 90 \pm 14 days post-procedure was 42.03% in the IVT followed by EVT group and 26.14% in the EVT alone group. Based on the superiority hypothesis, the study aims to determine whether the favorable outcome rate (90-day mRS ≤ 2) in the IVT followed by EVT group is superior to that in the EVT alone group. Assuming a one-sided type I error rate of 0.025 and 80% statistical power, and using a 1:1 randomization ratio, the required sample size is 136 patients per group (a total of 272 patients). Considering an anticipated dropout rate of approximately 20%, the final sample size is adjusted to 340 patients, with 170 patients per group.

This study hypothesizes that IVT followed by EVT is superior to EVT alone. However, given the limited reference data and clinical evidence in the anterior circulation indicating that EVT alone may be non-inferior to IVT followed by EVT, an interim analysis is planned after one-third (114) of the patients have completed follow-up for the primary endpoint. During the interim analysis, the DSMB will evaluate the efficacy data from both groups and conduct a sample size re-estimation based on the conditional power calculated from the available data. The DSMB will provide recommendations to the BEST-BAO research team on adjustments to the sample size or modifications to the study hypothesis.

If the efficacy advantage of the IVT followed by EVT group over the EVT alone group is less than anticipated, the sample size may be expanded appropriately, with an upper limit of no more than 20% of the original sample size. If the efficacy of the two groups appears to be similar, the study design will shift to a non-inferiority framework, evaluating whether EVT alone is non-inferior to IVT followed by EVT. Assuming similar efficacy (with both groups achieving a 90-day mRS score ≤ 2 in 42.03% of patients), the current sample size of 170 patients per group provides 80% power to test non-inferiority, with a one-sided type I error rate of 0.025 and a non-inferiority margin of -15%. The interim analysis and sample size re-estimation will be conducted under the strict control of the DSMB to ensure that the type I error rate is not inflated.

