10.4 Interim analysis

An interim analysis will be conducted after one-third (114) of the patients have completed follow-up for the primary endpoint, with the primary objective of reassessing the sample size. The DSMB will calculate the conditional power based on the available data and provide recommendations to the research team regarding any potential adjustments to the sample size. If the efficacy advantage of the IVT followed by EVT group over the EVT alone group is less than anticipated, the sample size may be expanded appropriately, with an upper limit of no more than 20% of the original sample size. If the efficacy of the two groups appears to be similar, the study design will shift to a non-inferiority framework, evaluating whether EVT alone is non-inferior to IVT followed by EVT.

The study does not include predefined conditions for early termination, except in cases where the DSMB recommends stopping the trial for safety reasons. Otherwise, enrollment will continue until the target sample size is achieved.

11. Quality control and quality assurance

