### 1.5 Sample size

Currently, no large-scale randomized controlled trials (RCTs) exist in this field. Therefore, the calculation of the sample size for this study will be based on the results of the RESCUE-RE registry study conducted in the Chinese population. According to the study, the proportion of patients achieving a mRS score  $\leq 2$  at 90 days post-procedure was 42.03% in the IVT followed by EVT group and 26.14% in the EVT alone group.

Based on the superiority hypothesis, the study aims to determine whether the proportion of patients achieving a modified Rankin Scale (mRS) score of  $\leq 2$  at 90 days is higher in the IVT followed by EVT group compared to the EVT alone group. The statistical hypotheses are defined as follows:

Null Hypothesis  $H_0: p_T - p_C \leq 0$

Alternative Hypothesis  $H_1: p_T - p_C > 0$

$\alpha = 0.025$  (per side),

Assuming a one-sided type I error rate of 0.025 and a statistical power of 80%, with equal allocation between the two groups (1:1), each group will require 136 patients (a total of 272 patients). Considering an anticipated dropout rate of approximately 20%, the final sample size will be adjusted to 340 patients, with 170 patients per group.

Given limited reference data and evidence suggesting the non-inferiority of EVT alone in the anterior circulation, an interim analysis will be conducted after one-third (114) of patients have completed follow-up for the primary endpoint. At this stage, the Data and Safety Monitoring Board (DSMB) will perform a sample size re-estimation based on the efficacy data obtained from both groups.

If the interim analysis the efficacy of the two groups is found to be similar, the study hypothesis will be adjusted to a non-inferiority hypothesis, aiming to verify whether EVT alone is non-inferior to IVT followed by EVT. The specific statistic hypotheses are as follows:

Null Hypothesis  $H_0: p_T - p_C \leq -\Delta$

Alternative Hypothesis  $H_1: p_T - p_C > -\Delta$

$\alpha = 0.025$  (per side),

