## 3.4 Interim Analysis

An interim analysis is planned once 1/3 (114 subjects) of the total population has completed the follow-up for the primary endpoint. During this interim analysis, the DSMB will conduct a sample size re-estimation based on the efficacy data obtained from both groups.

If the efficacy advantage of the IVT followed by EVT group over the EVT alone group is less than anticipated, the sample size will be appropriately increased. The DSMB will calculate the **conditional power** from the current data and provide recommendations to the BEST-BAO research team regarding sample size adjustments or modifications to the study hypothesis. The maximum increase in sample size will not exceed 20% of the original planned sample size.

If the efficacy of the two groups is found to be similar, the study hypothesis will be adjusted to a **non-inferiority hypothesis** to determine whether EVT alone is non-inferior to IVT followed by EVT. Assuming both groups achieve similar efficacy, with 42.03% of patients achieving a 90-day mRS  $\leq 2$ , and with a one-sided type I error rate of 0.025 and a non-inferiority margin of -15%, the current sample size of 170 patients per group will provide 80% power to demonstrate non-inferiority.

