#### 3.9.1 Primary efficacy endpoint

The primary efficacy endpoint, "the proportion of patients with mRS  $\leq 2$  at 90 days after onset," will be statistically described by treatment group. The 95% confidence intervals (CIs) will be calculated using the exact Clopper-Pearson method. Additionally, a bar chart will be used to display the distribution of mRS scores.

When using a superiority hypothesis test, the specific statistical hypotheses are as follows:

Null hypothesis  $H_0: p_T - p_C \leq 0$

Alternative hypothesis  $H_1: p_T - p_C > 0$

$\alpha = 0.025$  (one side)

If the hypothesis is adjusted to a non-inferiority hypothesis after the interim analysis, the specific statistical hypotheses are as follows:

Null hypothesis  $H_0: p_T - p_C \leq -15\%$

Alternative hypothesis  $H_1: p_T - p_C > -15\%$

$\alpha = 0.025$  (one side)

Here,  $p_T$  represent the proportions of patients with mRS  $\leq 2$  in the IVT followed by EVT and EVT alone groups, respectively.

A log-binomial model will be used, assuming the primary endpoint follows a binomial distribution. A log-link function will be applied, with covariates including age, pre-stroke mRS, time from onset to randomization, stroke severity (NIHSS score), and collateral circulation. Adjusted and unadjusted risk difference (RD) and risk ratio (RR) with their 95% confidence intervals will be reported.

For superiority, if the lower bound of the 95% CI of the adjusted RD  $> 0$ , superiority is established.

For non-inferiority, if the lower bound of the 95% CI of the adjusted RD  $> -15\%$ , non-inferiority is established.

Additionally, Chi-square tests (expected cell count  $\geq 5$ ), continuity-corrected chi-square tests (1 expected cell count between 1 and 5), or Fisher's exact test ( $\geq 1$  expected cell count  $< 5$  or any expected cell count  $< 1$ ) will also be used for group comparisons, and P-values will be reported.

The mRS score used in the primary analysis will be based on centralized assessments. If centralized assessments are missing for certain subjects, local investigator assessments will be used by default. Sensitivity analyses will also use local assessments to evaluate the robustness of the results.

A list of all primary efficacy endpoint data for all visits (m-ITT, AT, PPS sets) will be provided.

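### SAP 3.3 rules out a multiplicity issue because there is no early efficacy stop, but an increase in N based on the unblinded difference followed by the ordinary 95% CI has no stated error control; the possible excess is small and conditional

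*SAP*

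**What the plan says.** SAP 3.3 consists of one argument: "This study does not involve early termination due to efficacy during interim analysis. Therefore, there are no issues related to multiplicity".

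SAP 3.4 describes a single interim look after 114 patients have completed primary follow-up. The DSMB re-estimates the sample size from the efficacy data of both groups, so the look is comparative and unblinded. When the advantage of IVT followed by EVT "over the EVT alone group is less than anticipated, the sample size will be appropriately increased", by at most 20%. If efficacy looks similar, the hypothesis changes to non-inferiority of EVT alone.

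Protocol 10.4 has the same two branches, but there "the sample size may be expanded appropriately, with an upper limit of no more than 20% of the original sample size". Protocol 10.1 adds that the interim analysis and re-estimation will run "under the strict control of the DSMB to ensure that the type I error rate is not inflated".

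The final criterion in SAP 3.9.1 is unchanged by the interim: superiority is established "if the lower bound of the 95% CI of the adjusted RD" exceeds zero.

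**The concern.** An efficacy stop is only one way in which an interim look can raise type I error. Another is to let the final N depend on the observed treatment difference and then analyse as if N had been fixed. SAP 3.3 deals with the first and concludes that the second is absent.

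Neither document names a combination test, fixed stage weights, a conditional-power zone or an adjusted critical value. DSMB oversight is a governance arrangement and does not control the error rate. The trigger for enlargement has an upper edge (the anticipated advantage) but no lower one, so as worded it includes interim results for which adding patients raises the chance of a false positive.

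At stake is the standing of the superiority claim. A borderline positive result after an enlargement could be challenged because the error rate was asserted without a supporting method.

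**Working it through.** **Inputs.** Rates of mRS ≤ 2: "42.03% in the IVT followed by EVT group and 26.14% in the EVT alone group" (SAP 1.5), a difference of 15.89 points; one-sided alpha 0.025, power 80%, 1:1 (SAP 1.5); N = 340 (SAP 1.5); interim at 114, cap 20% (SAP 3.4), so 340 × 1.2 = 408; ordinary 95% CI at the end (SAP 3.9.1).

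**1. The plan's own figure.** Variance sum = 0.4203 × 0.5797 + 0.2614 × 0.7386 = 0.4367. Then n = (1.960 + 0.842)² × 0.4367 / 0.1589² = 135.8, so 136 per group; 272 / 0.80 = 340. Both are reproduced.

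**2. The trigger on the z scale.** Interim SE = sqrt(0.4367 / 57) = 0.0875. A difference of 15.89 points is z = 0.1589 / 0.0875 = 1.815.

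**3. Where enlargement raises the error.** Given interim z1, the null probability of final rejection with the ordinary test is

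A(z1, N) = 1 − Φ[(1.96·√N − z1·√114) / √(N − 114)].

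A(z1, 408) exceeds A(z1, 340) when z1 < 1.086, which is 1.086 × 0.0875 = 9.5 points. Above that, enlargement lowers the error. The written trigger covers both regions.

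**4. Overall one-sided alpha**, integrating A over z1 ~ N(0,1):

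| Rule, ordinary final test | Alpha |
|---|---|
| Fixed N = 340 | 0.0250 |
| To 408 whenever the difference is below 15.89 points | 0.0260 |
| Worst case under the 20% cap (to 408 if z1 < 1.086) | 0.0264 |

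Measured against the 272 evaluable patients instead of 340, the last two become 0.0263 and 0.0267.

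**5. The *similar* branch.** The word is undefined, so the zones below are assumptions, with N going to 408 elsewhere below 15.89 points.

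| Assumed zone (absolute difference) | No enlargement in zone, superiority still claimable | Switch binding, superiority barred |
|---|---|---|
| < 1 point | – | 0.0250 |
| < 2 points | 0.0255 | 0.0240 |
| < 5 points | 0.0250 | 0.0209 |

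**6. Binomial check** (4 million trials per rate, Wald CI, common rates 26% to 42%). The fixed design gives 0.0253 to 0.0271; enlargement below 15.89 points gives 0.0262 to 0.0268. Discreteness is as large as the effect, so the integration is what isolates it.

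**7. Candidate remedies**, with power at the planning effect (mean z1 = 1.815, all randomised patients evaluable):

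| Design | Alpha | Power |
|---|---|---|
| Fixed 340 | 0.0250 | 88.0% |
| Enlarge below 15.89 points, ordinary test | 0.0260 | 92.3% |
| Same enlargement, fixed weights | 0.0250 | 92.0% |
| Enlarge only if conditional power is 50% to 80%, ordinary test | 0.0248 | 88.8% |

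The zone in the last row uses current-trend conditional power at N = 340. It equals 50% at z1 = 1.96 × sqrt(114/340) = 1.135 (9.9 points) and 80% at z1 = 1.532 (13.4 points).

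**The case against.** The strongest reply is that step 4 models half of one interim rule. Results judged similar go to non-inferiority, a branch powered at the existing 170 per group with no enlargement mentioned. Step 5 shows that this can remove the excess. This stands, and it makes the inflation conditional. It does not rescue SAP 3.3: *similar* has no definition, no text orders the two branches or bars a later superiority claim, and under protocol 9.4 the sponsor may decline a DSMB recommendation.

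Second, the DSMB computes conditional power and recommends; going to the cap below 15.89 points is a modelling choice. Protocol 9.4 also refers to a DSMB charter that is not among the documents and might hold thresholds. This too stands, and it limits confidence about the rule that will operate. Even so, SAP 3.3 gives the absence of an efficacy stop as its reason, and that reason is wrong whatever the charter says.

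Third, the excess is at most 0.0014 (0.0017 on the 272 basis). True, and it bounds the importance of the point.

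A reader might infer that the plan would add 68 patients at an interim difference of zero. The documents do not support that as the expected course: a zero difference is the clearest case of similar efficacy, which they send to non-inferiority.

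**Conclusion.** The inference in SAP 3.3 is wrong, and the protocol's assurance on type I error has no method behind it in either document. Under the literal enlargement trigger alone, one-sided alpha is about 0.0260, with a ceiling of 0.0264 under the 20% cap (0.0263 and 0.0267 on the 272 basis).

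A reader might go further and conclude that this trial's error rate is definitely inflated. The documents do not establish that. The excess shrinks or vanishes if similar results are not enlarged, and superiority alpha falls below 0.025 if the switch is binding and the zone is wider than about 1 point. The supportable statement is that the achieved error rate cannot be determined from the plan, although the plan says it is controlled.

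The figures assume a normal approximation, 57 patients per group at the interim, an increase to the full cap, and the stated zones for *similar*. Confidence is medium. The plan should be changed, but the size of the effect does not by itself threaten the trial.

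**What to change.** Delete the SAP 3.3 inference and prespecify one rule in SAP 3.3, SAP 3.4 and protocol 10.4, before interim comparative data are seen.

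- **Preferred.** Allow the increase, and base the superiority test and its CI on the stagewise adjusted estimates combined with fixed weights sqrt(114/340) and sqrt(226/340), whatever the final N. Alpha is 0.0250; power falls only from 92.3% to 92.0%. The cost is that SAP 3.9.1 must specify the stagewise adjusted estimates and the CI built from them.
- **Simpler variant.** Keep the ordinary estimate but use a critical value of about 1.984 (about 1.988 on the 272 basis), which holds 0.025 against any enlargement up to 20%.
- **Alternative.** Increase only if current-trend conditional power at N = 340 is at least 50% and below 80% (about 9.9 to 13.4 points). The ordinary CI then stays valid (alpha 0.0248). The cost is most of the power gain: 88.8% against 92.3%. It also gives up increases between 13.4 and 15.9 points, where conditional power is 80% to 93%.

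Under any option, define *similar* numerically, state that the non-inferiority branch is applied first and whether it bars a later superiority claim, and reconcile *will be* in SAP 3.4 with *may be* in protocol 10.4. Carry the same wording into the DSMB charter.

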## 3.4 Interim Analysis

An interim analysis is planned once 1/3 (114 subjects) of the total population has completed the follow-up for the primary endpoint. During this interim analysis, the DSMB will conduct a sample size re-estimation based on the efficacy data obtained from both groups.

If the efficacy advantage of the IVT followed by EVT group over the EVT alone group is less than anticipated, the sample size will be appropriately increased. The DSMB will calculate the **conditional power** from the current data and provide recommendations to the BEST-BAO research team regarding sample size adjustments or modifications to the study hypothesis. The maximum increase in sample size will not exceed 20% of the original planned sample size.

If the efficacy of the two groups is found to be similar, the study hypothesis will be adjusted to a **non-inferiority hypothesis** to determine whether EVT alone is non-inferior to IVT followed by EVT. Assuming both groups achieve similar efficacy, with 42.03% of patients achieving a 90-day mRS  $\leq 2$ , and with a one-sided type I error rate of 0.025 and a non-inferiority margin of -15%, the current sample size of 170 patients per group will provide 80% power to demonstrate non-inferiority.

## 3.5 Trial completion and subject distribution analysis

Based on the screening population, the trial will summarize the screening process and reasons for screening failures. Using the randomized population (ITT set), the trial will summarize randomization and trial completion, including reasons for early termination. The number and percentage of subjects in each treatment group and site will be calculated. A list of subjects who failed screening will be provided, along with a list of all randomized subjects and their clinical trial completion status (ITT set).

The inclusion of subjects in each analysis dataset (m-ITT, PPS, SS) will also be summarized based on the randomized population (ITT set), with the number of subjects in each dataset calculated by treatment group and site. A list of all subjects included in the analysis datasets (ITT set) will also be provided.

The trial will summarize major protocol deviations based on the randomized population (ITT set), with the number and percentage of subjects with major protocol deviations calculated by treatment group. A list of all subjects with major protocol deviations (ITT set) will be provided.

A subject distribution flowchart will also be created.

### 3.6 Demographic and baseline analysis

Demographic and other baseline characteristic analyses will be performed based on the m-ITT population.

Baseline demographic characteristics (e.g., age, sex, ethnicity, height, weight) will be statistically described by treatment group. Vital signs, baseline imaging data, and laboratory test results will also be described by treatment group. A list of all subjects' baseline demographic data (m-ITT set) will be provided.

Previous medical history and current medical history will be coded using the **medical dictionary for regulatory activities (MedDRA V25.0)** and classified by **system organ class (SOC)** and **preferred term (PT)**. Previous/concomitant medical history will be summarized by SOC and PT, with the number and percentage of subjects in each category calculated by treatment group. A list of all subjects' past/concomitant medical history (m-ITT set) will be provided.

### 3.7 Concomitant medications, treatments, and previous procedures/surgeries

Concomitant medications and treatments/procedures during the clinical trial are defined as all non-investigational or control interventions/drugs and other treatments used during the clinical trial period.

Previous procedures/surgeries are defined as those with an end date earlier than the first administration of the investigational drug.

Previous and concomitant treatments/procedures during the clinical trial will be coded using the **MedDRA V25.0** and **SOC** and **PT**. Previous concomitant medications and concomitant medications during the study will be coded using the **world health organization drug dictionary (WHODrug Global 2022.03)**, with appropriate medication terms and ATC codes selected.

Based on the m-ITT analysis set, previous treatments/procedures will be summarized by SOC and PT, with the number and percentage of subjects calculated by treatment group. A list of all subjects' past treatments/procedures (m-ITT set) will be provided.

Based on the m-ITT analysis set, concomitant treatments/procedures during the clinical trial will be summarized by SOC and PT, with the number and percentage of subjects calculated by treatment group. Concomitant medications will be summarized using ATC codes, with the number and percentage of subjects calculated by treatment group. A list of all subjects' concomitant medications and treatments/procedures during the clinical trial (m-ITT set) will be provided.

### 3.8 Use of thrombolytic drugs and thrombectomy Procedures

Using the m-ITT set, the actual dosage, type, and administration time of IVT thrombolytic drugs will be described.

Additionally, based on the m-ITT set, the timeline for each treatment stage will be described by treatment group, including time from symptom onset to emergency admission, CT/MR, randomization, initiation of IVT, initiation of EVT, first successful reperfusion, and end of procedure. Details of vascular device types, specifications, quantities, and usage sequence will be recorded, as well as the type of anesthesia (if used) and sedation.

Vascular recanalization outcomes, post-procedure diagnoses, eTICI grading, collateral circulation scores, and other relevant data will also be described by treatment group.

A list of all subjects' thrombolytic drug use and thrombectomy procedure details (m-ITT set) will be provided.

